10.3 Clinical Laboratory Evaluation

Hematology, serum chemistry and coagulation laboratory parameters will be summarized using descriptive statistics at baseline, Day 7, Day 28, Month 3, Month 6, and Month 12/Early Term. Change from baseline in the laboratory parameters will also be presented, Unless otherwise noted, baseline is defined as the value obtained at the baseline visit. If the baseline value is missing, the baseline value will be the last nonmissing value recorded prior to the first dose of study drug.

No concerns are expected regarding the drug for laboratory results since the drug is expected to stay in the eye. As a result, no analysis using high/low flags will be carried out.

Urinalysis results will not be summarized but will be provided in data listing. Separate listing of abnormal clinically significant lab values and ECG interpretation will be presented.

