The investigational product (jCell) is a live suspension of $0.5-3.0 \times 10^6$ human retinal progenitor cells (hRPC) suspended in clinical grade medium. The hRPC are of allogeneic human fetal origin. Study subjects will receive a single dose of either 0.5, 1.0, 2.0, 3.0 x 10^6 jCell as an intravitreal injection under topical anesthesia into the eye with the worst visual acuity.

Duration of treatment:

Treatment with jCell consists of a single intravitreal injection. The injection procedure itself takes approximately 2 minutes. Patients will be released to home on the day of injection. Study subjects will be followed for one year post-injection under this protocol with a separate protocol planned for two additional years of long term follow up.

Criteria for Evaluation:

Efficacy:

Efficacy will be assessed based on a series of ophthmalogic assessments at specified timepoints, including best corrected visual acuity (BCVA), spectral domain optical coherence tomography (OCT), electroretinogram (ECG), visual field testing (where appropriate), fluorescein angiography, autofluorescence and a visual quality of life

NAME OF COMPANY: jCyte, Inc	SUMMARY TABLE	(For national Authority Use Only)
NAME OF FINISHED PRODUCT: iCell	Volume:	
NAME OF ACTIVE INGREDIENT:	Page:	
human retinal progenitor cells	Reference:	

questionaire (VFQ-25). In addition, several low vision assessment tools may be explored in subsets of subjects in order to better understand which assessments may be most useful for this type of treatment approach. None of these assessments are invasive.

Safety:

Safety will be assessed on an ongoing basis by adverse events, identification of dose-limiting toxicities (if any), physical examinations and vital signs, clinical laboratory values, and anti-drug antibodies. In addition, specific ophthalmalogic tests to monitor safety will be performed, including slit lamp and fundus examiniation, B-scans and intraocular pressure (IOP). Additional ophthalmalogic tests described above will also contribute to safety monitoring.

Clinical safety data will be reviewed on an ongoing basis. Safety data will undergo formal review by a DSMB following completion of each dose level 1 in Cohort 1 before initiation of the next dose level in Cohort 1, and before the initiation of the same dose level in Cohorty 2.

Statistical methods:

Background and demograhic data will be summarized for all subjects using descriptive statistics.

Efficacy:

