4.0 SUBJECT SELECTION

4.1 Inclusion Criteria

The following conditions must be met before a subject may be enrolled in the study.

- 1. Willing to give written informed consent, able to make the required study visits and follow study protocol instructions.
- 2. Willing to consent to gene mutation typing. Mutation typing will be restricted to typing for eye disease-related genes known to be involved in inherited retinal degenerations and related disorders. If typing results are already available for the subject, the previous results can be recorded and this requirement is waived.
- 3. Clinical diagnosis of RP confirmed by ERG.
- 4. BCVA 20/200 or worse and no worse than HM in cohort 1; and BCVA 20/40 or worse and no worse than 20/200 for the second cohort.
- 5. Male or female, age \geq 18 yr.
- 6. Adequate organ function:
 - a. blood counts (hematocrit, Hgb, WBC, platelets and differential) within normal range, or if outside of normal range, not clinically significant as judged by the investigator
 - b. liver function: alanine transaminase [ALT] and aspartate transaminase [AST] ≤2 times the upper limit of the normal range
 - c. total bilirubin ≤ 1.5 times the upper limit of the normal range

- d. renal function: serum creatinine ≤1.25 times the upper limit of the normal range
- 7. Negative infectious disease screen (hepatitis B, C or HIV); and drugs of abuse (negative urine screen).
- 8. A female patient of childbearing potential (not surgically sterilized and less than one year postmenopausal) must have a negative pregnancy test (urine human chorionic gonadotropin) at entry (prior to injection), and must have used medically accepted contraception for at least one month prior to treatment. Note: Women of childbearing potential and men must be advised to use a medically accepted method of contraception for at least 12 months following treatment.
- 9. Willing to provide a blood sample for HLA typing, if not done previously with available results

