5. GENERAL ANALYSIS CONSIDERATIONS

The statistical analyses will be reported using summary tables and listings (TLs). The International Conference on Harmonization (ICH) numbering convention will be used for all TLs. Continuous variables will be summarized with means, standard deviations, medians, minimums, and maximums. Categorical variables will be summarized by counts and by percentage of subjects in corresponding categories. Percentages for missing values are omitted and do not account for the percent calculation of other categories. Percentages are routinely based on the total category count excluding the missing category if not otherwise mentioned. Percentages showing a rate relative to the total number of subjects in this group are given in special tables (e.g. AE tables). Footnotes will specify the percent basis. All summary tables will be presented by cohort and dose level. Baseline summaries will also include a total summary column. Unless otherwise noted, baseline is defined as the value obtained at the baseline visit. If the baseline value is missing, the baseline value will be the last non-missing value recorded prior to the first dose of study drug.

Individual subject data obtained from the case report forms (CRFs) and derived data will be presented by subject in data listings.

jCyte, Inc	Statistical Analysis Plan
Protocol No. JC-01	08Nov2017

The analyses described in this plan are considered *a priori*, in that they have been defined prior to database lock. Post-hoc analyses will be labeled as such on the output and identified in the CSR.

All analyses and tabulations will be performed using SAS[®] Version 9.4 or higher. Tables, listings, and figures will be presented in RTF format. Upon completion, all SAS[®] programs will be validated by an independent programmer. In addition, all program output will undergo a senior level statistical review. The validation process will be used to confirm that statistically valid methods have been implemented and that all data manipulations and calculations are accurate. Checks will be made to ensure accuracy, consistency with this plan, consistency within tables, and consistency between tables and corresponding data listings. Upon completion of validation and quality review procedures, all documentation will be collected and filed by the project statistician or designee.

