Cohort 2 - $0.5 \ge 10^6$ hRPC	XXXXXX	2							
				Listia	a 16 2 9 1				

Listing 16.2.8.1 Hematology Part 2 of 2

					Lymphocytes					Lymphocytes	5	Eosiophils	
	Subject		Collection	Neutrophils	(%)	Monocytes	Eosinophils	Basophils	Neutrophils	(x 10^3/uL)	Monocytes	(x 10^3/uL)	Basophils
Treatment Group	ID	Visit	Date/Time	(%)		(%)	(%)	(%)	(x 10^3/uL)		(x 10^3/uL)		(x 10^3/uL)

Note: L=Low and H=High, CS=Clinically Significant . path\l program.sas date time

Programmer Note: If NO marked for examination, include reason in "Examination Date" column.

Listing 16.2.8.2 Chemistry Part 1 of 2

Treatment Group	Subject ID	Visit	Collection Date (Study Day)	Collection Time	Bilirubin (mg/dL)	Sodium (mmol/L))	Potassium (mmol/L)	Chloride (mmol/L)	Bicarbonate (mmol/L)	ALT (U/L)	AST (U/L)	Alkaline Phosphatase (U/L)
Cohort 1 $0.5 \times 10^6 h PPC$	VVV VVV	Screening	Date((vv)	Time5								
	лллллл	Baseline	Date $Q_{\rm L}(\mathbf{x}\mathbf{x})$	Time5								
		Day 7	Date 9. (XX)	Time5.								
		Day /	Dates. (XX)	Times.								
		Day 28	Date9. (xx)	Time5.								
		Month 3	Not Done:									
			Reason									
		Month 6	Date9. (xx)	Time5.								
		Month 12 or	Date9. (xx)	Time5.								
		Early	- ()									
		Termination										

Cohort 2 - 0.5 x 10⁶ hRPC xxx--xxx

Listing 16.2.8.2 Chemistry Part 2 of 2

			Collection								
	Subject		Date (Study	Collection	BUN	Creatinine	Total Protein	Albumin	Calcium	Phosphate	Glucose
Treatment Group	ID	Visit	Day)	Time	(mg/dL)	(mg/dL)	(g/dL)	(g/dL)	(mg/dL)	(mg/dL)	(mg/dL)

Cohort 1 - 0.5 x 10⁶ hRPC xxx--xxx Screening Date9. (xx) Time5.

Note: L=Low and H=High, CS=Clinically Significant. path\l_program.sas date time

Programmer Note: If NO marked for examination, include reason in "Examination Date" column.

Listing 16.2.8.3 Coagulation

Treatment Group	Subject ID	Visit	Collection Date/ (Study Day)	Collection Time	PT (sec)	PTT (sec)	INR	Coagulation Results Abnormal?/if Yes: Abnormatlity
Cohort 1 - 0.5×10^6 hRPC	xxxxxx	Screening	Date9. (xx)	Time5.				Yes: NCS
		Baseline	Date9. (xx)	Time5.				1.00
		Day 7	Date9. (xx)	Time5.				No
		Day 28	Date9. (xx)	Time5.				Yes: CS
		Month 3	Date9. (xx)	Time5.				
		Month 6	Date9. (xx)	Time5.				
		Month 12 or Early	Date9. (xx)	Time5.				
		Termination						

Cohort 2 - 0.5 x 10⁶ hRPC xxx--xxx

.....

Note: CS=Clinically Significant. path\l_program.sas date time

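### SAP 10.3 rules out high/low laboratory analysis on an expectation, and the tables that remain cannot in general count the subjects newly abnormal after injection

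*SAP*

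**What the plan says.** **Laboratory values as a safety assessment.** The protocol synopsis (Criteria for Evaluation, Safety) states: "Safety will be assessed on an ongoing basis by adverse events, identification of dose-limiting toxicities (if any), physical examinations and vital signs, clinical laboratory values". Protocol 10.3 promises descriptive statistics for laboratory parameters and nothing more specific.

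**Who may enter.** Protocol 4.1, criterion 6, allows "liver function: alanine transaminase [ALT] and aspartate transaminase [AST] ≤2 times the upper limit of the normal range". It also allows bilirubin up to 1.5 times and creatinine up to 1.25 times the upper limit, and out-of-range blood counts if the investigator judges them not clinically significant.

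**Planned tables.** SAP 10.3: "Hematology, serum chemistry and coagulation laboratory parameters will be summarized using descriptive statistics at baseline" and at Day 7, Day 28, Month 3, Month 6 and Month 12/Early Term, with change from baseline. SAP section 5: "Continuous variables will be summarized with means, standard deviations, medians, minimums, and maximums", and "All summary tables will be presented by cohort and dose level". The shells for Tables 14.3.4.1 to 14.3.4.3 follow this. They show no reference limits, out-of-range counts or shifts.

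**The exclusion.** SAP 10.3 continues: "No concerns are expected regarding the drug for laboratory results since the drug is expected to stay in the eye". Then: "As a result, no analysis using high/low flags will be carried out".

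**What else is reported.** The hematology and chemistry listings (16.2.8.1 and 16.2.8.2) carry the footnote "Note: L=Low and H=High, CS=Clinically Significant". Listing 16.2.8.5 is confined to clinically significant values. A laboratory finding reported as an adverse event would be counted in the TEAE tables.

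**The concern.** The reason given for leaving out the analysis is an expectation about where the product stays. The documents do not treat that expectation as settled. Protocol 1.1.3 says allogeneic grafts in immune-privileged sites can still be rejected. Protocol 8.1.4 tests blood for panel- and donor-reactive antibodies. Protocol 1.3 describes earlier human use in three patients at 500,000 cells each, reports no laboratory results for them, and says the cells may not fully represent the present product. This study goes to 3 million cells (3,000,000 / 500,000 = 6 times that dose).

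Safety and tolerability is the primary objective. The basic laboratory question is how many subjects were in range before injection and out of range after it. Because criterion 6 admits subjects already out of range, a high post-injection maximum may be an entry value. If the tables cannot separate the two, the report gives no count for this part of the primary objective.

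**Working it through.** The plan states no figure to reproduce here: the sample size has no formal basis and no hypothesis is tested. The planned number adds up: 2 cohorts × (4 + 4 + 3 + 3) = 28. The check is whether the planned statistics determine the number of newly abnormal subjects.

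**1. A pair of data sets with identical tables.** Take one column of n = 3, one analyte and one post-injection visit. The upper limit of normal (ULN) of 40 is an assumption for illustration. The highest entry value is 42/40 = 1.05 × ULN, which criterion 6 allows for ALT or AST.

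| Subject | A: baseline → visit (change) | B: baseline → visit (change) |
|---|---|---|
| 1 | 32 → 32 (0) | 32 → 40 (+8) |
| 2 | 34 → 42 (+8) | 34 → 32 (−2) |
| 3 | 42 → 40 (−2) | 42 → 42 (0) |
| Newly above 40 | 1 | 0 |

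Both sets have baseline values {32, 34, 42}, visit values {32, 40, 42} and changes {−2, 0, 8}. Every planned statistic is therefore the same:

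- Baseline: mean 36, median 34, min 32, max 42.
- Visit: mean 38, median 40, min 32, max 42.
- Change: mean 2, median 0, min −2, max 8.
- SD: √(56/2) = 5.29 in all three rows (sums of squares 16+4+36, 36+4+16 and 16+4+36).

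A four-subject pair also exists. Baseline 32, 32, 34, 42 can become 32, 32, 42, 40 (one newly high) or 32, 40, 32, 42 (none), with the same visit values and the same changes {−2, 0, 0, 8}.

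**2. Why this happens.** Let h0 be the number above the limit at baseline and h1 the number above it at the visit. If a reader can recover both, the number newly high lies between max(0, h1 − h0) and min(h1, n − h0). In the pair above h0 = h1 = 1 and n = 3, so the bounds are 0 and min(1, 2) = 1. At a single visit the ambiguity needs at least one subject out of range at entry. Visits are not linked to each other either. If all three subjects start at 32 and both Day 7 and Day 28 show {32, 32, 42}, one subject or two may have become high.

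**3. How often a column contains an out-of-range entry value.** The documents give no rate, so a range is assumed. P(at least one of n) = 1 − (1 − p)^n.

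| p | n = 4 | n = 28 |
|---|---|---|
| 5% | 19% | 76% |
| 10% | 34% | 95% |
| 20% | 59% | 99.8% |

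These figures show how often the precondition in step 2 holds for one analyte. They do not measure missed harm.

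**4. What a shift table could support.** Exact (Clopper-Pearson) 95% intervals: 0/3 is 0 to 70.8%, 0/4 is 0 to 60.2%, 1/4 is 0.6 to 80.6%, 0/28 is 0 to 12.3%, and 1/28 is 0.1 to 18.3%.

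**5. Coagulation.** Protocol 7.5.3, 7.5.6, 7.5.8 and 7.5.11 repeat coagulation at Day 7, Day 28, Month 3 and Month 6 only in subjects abnormal at baseline. Protocol 7.6 has no such restriction at Month 12/Early Termination. A subject normal at baseline can therefore show a new abnormality only at that last visit. The Table 2 footnote lists the coagulation panel among the safety laboratory tests without the restriction.

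**The case against.** **The tables often suffice.** In columns this small, the summary statistics nearly give back the data. With n = 3 the minimum, median and maximum are all three values. With n = 4, adding the SD recovers the fourth, apart from rounding. Suppose ALT in units of ULN goes from 1.8, 0.5, 0.5, 0.5 to 1.8, 0.5, 0.5, 1.7. The maximum stays at 1.8, but the median moves from 0.5 to 1.1 and the visit SD is 0.72, so a reader who knows the limit can recover 0.5, 0.5, 1.7, 1.8 and see at least one new case. This stands. The tables fail through the missing link between baseline and visit, chiefly when one subject normalises as another becomes abnormal. The reader must also supply limits that the shells lack.

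**The information is in the report.** The hematology and chemistry listings show each subject's values by visit, grouped by cohort and dose, with L/H codes. For at most 28 subjects the count can be made by hand. This also stands and is the main reason the point is modest. Listing 16.2.8.5 and the TEAE tables are weaker substitutes, because both depend on an open-label investigator's judgement that a value is significant or untoward.

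**No commitment is broken.** Protocol 10.3 asks only for descriptive statistics, and the SAP supplies them. A reader might infer that the SAP contradicts the protocol, or that it fixes a finding of no concern whatever the data show. The documents support neither reading: SAP 10.3 states an expectation and omits one display, but prescribes no conclusion.

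**Conclusion.** The point holds as a modest gap in summary presentation. SAP 10.3 excludes high/low analysis on an expectation alone, and the tables left in place cannot in general give the number of subjects newly out of range. The n = 3 pair proves this. It assumes a ULN of 40 only for illustration; the argument needs only one entry value above the limit, which criterion 6 permits.

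Two stronger readings should be resisted. The tables do not always hide new abnormalities, and no laboratory data are lost. Nor would a high/low analysis show whether abnormalities rise with dose. With 3 or 4 subjects per column, and 1/4 compatible with anything from 0.6% to 80.6%, the counts would be descriptive and could not establish a trend.

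**What to change.** In SAP 10.3, delete the two sentences that state the expectation and exclude the flag analysis. Add one shift table each for hematology and chemistry, beside Tables 14.3.4.1 and 14.3.4.2, specified as follows:

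- Safety population, by cohort, dose level and Total, with the number evaluable.
- From Low, Normal or High at baseline to the post-baseline category, using the L/H codes already planned for Listings 16.2.8.1 and 16.2.8.2.
- A subject with both low and high post-baseline values is counted in each direction.
- Change-from-baseline summaries and the clinically significant listing are kept, because worsening within the High category (for example 1.8 to 3.0 × ULN) does not appear as a shift.
- Any coagulation shift is limited to Month 12/Early Termination while the 7.5 visit sections stand as written. Those sections and the Table 2 footnote must be reconciled.

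**Cost.** SAP wording and two programmed tables (three if coagulation is included). No new data, visits or subjects.

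**Downside.** Some shifts will arise by chance. Assume each draw is out of range with probability q, independently. The chance that a subject is normal at baseline and out of range at one or more of five visits is (1 − q)(1 − (1 − q)^5). For q = 5% this is 0.95 × 0.226 = 21% per analyte, and 1 − (1 − 0.215)^4 = 62% for at least one such subject in a column of 4. For q = 10% it is 0.90 × 0.410 = 37%, and 1 − (1 − 0.369)^4 = 84%. Correlation between a subject's draws lowers these figures, but the shells list about 29 analytes. The tables should therefore be read beside the clinically significant listing and labelled descriptive.

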10.4 Vital Signs

Vital signs (systolic BP, diastolic BP, heart rate, respiration, temperature, and weight) will be summarized using descriptive statistics at baseline and at each post-baseline time point. Changes from baseline will also be summarized. Baseline is defined as the value obtained at the baseline visit. If the baseline value is missing, the baseline value will be the last non-missing value recorded prior to the first dose of study drug.

10.5 Physical Examination

Physical examination results will be included in data listings only.

10.6 Electrocardiogram

ECG parameters will be presented in a listing..

10.7 Ophthalmic AEs

10.7.1 Slit Lamp and Fundus Photography

Slit Lamp and Fundus Photography - The slit lamp exam will be summarized by eye structure. For eye structures of eyelids, eyelashes, conjunctiva, sclera, cornea, and iris, subjects will be tabulated by the categories of Normal, Abnormal NCS, and Abnormal CS at each time point, and percentages will be displayed. For anterior chamber flare, subjects will be tabulated by the flare grade and the categories of Abnormal NCS and Abnormal CS. For lens status, subjects will be tabulated as aphakic, pseudophakic, and phakic. For cataract type, subjects will be tabulated as nuclear, cortical, posterior sub capsular, and not applicable. Subjects will also be tabulated by grades of 1+, 2+, 3+ and 4+. For the fundus photography, subjects will be tabulated by the categories of Normal and Abnormal NCS and Abnormal CS. Results will be presented for each of subjects' eyes (study eye and non-study eye) at all time points.

If Clinically Significant value is not reported in the follow-up visit, then the value will be imputed based on the value of previous visit, consistent with CRF completion guidelines. For example, if abnormal change from previous visit is "NO" then imputed value will be value from the previous visit.

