3.2.2 Safety Endpoints

The primary goal of the study is to evaluate the safety and tolerability of jCell injection: The criteria that will be used to establish safety include:

- Slit-lamp findings, i.e., anterior chamber cell or flare; acute cataract development or progression in phakic patients, vitreous haze.
- Absence of tumor formation, overt immune rejection, decrease in BCVA attributable to treatment
- Absence of clinically significant, persistent increase in intraocular pressure (>10 mm Hg above baseline or IOP > 25 mm Hg), clinically significant epiretinal membrane, retinal detachment, neovascularization, or endophthalmitis
- No clinically significant adverse events attributable to investigational product (jCell) injection
- Patient comfort (no intolerable pain related to procedure)

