8.1.5 Ophthalmic AEs

Procedures will be performed at scheduled intervals to specifically assess eye AEs that may not be detected by usual AE reporting. Please refer to the study procedure manual for details of all ophthalmologic assessment procedures.

Slit lamp and fundus exam - The binocular slit-lamp examination provides a stereoscopic magnified view of the eye structures in detail, enabling anatomical diagnoses to be made for a variety of eye conditions. This assessment will include detection of anterior chamber cell or flare; acute cataract development or progression in phakic patients, or vitreous haze. Fundus exam allows for inspection of the retina, the cellular graft, and detection of retinal detachment.

B-scan – B-scan is a test that uses high-frequency sound waves to get measurements and produce detailed images of the eye. This test may provide information regarding the location of the injected cells and the size of the cell clusters at different time points during the study.

IOP - Intraocular pressure is measured with a tonometer as part of a comprehensive eye examination. Measured values of intraocular pressure are influenced by corneal thickness and rigidity

Spectral Domain Optical Coherence Tomography (OCT) - A clinical OCT machine will be used for data collection; the same machine should be used for any given patient at each time point. OCT tests, including assessment of the ellipsoid zone (EZ), will be analyzed to help define retinal anatomy, and will enable monitoring for ocular inflammation after treatment as manifest by cystoid macular edema or epiretinal membrane formation or progression.

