Not Applicable	n (%)	n (%)	n (%)	n (%)	n (%)
Grade					
Baseline ^[2]	(n=)	(n=)	(n=)	(n=)	(n=)
+1	n (%)	n (%)	n (%)	n (%)	n (%)
+2	n (%)	n (%)	n (%)	n (%)	n (%)
+3	n (%)	n (%)	n (%)	n (%)	n (%)
+4	n (%)	n (%)	n (%)	n (%)	n (%)
		<pre></pre>	\[<pre> / /</pre>	

Table 14.3.4.6.1 Slit Lamp Examination: Study Eye Safety Population

^[1] Total includes both Cohorts 1 and 2. ^[2] Baseline is defined as the value obtained at the baseline visit. If the baseline value is missing, the baseline value will be the last non-missing value recorded prior to the first dose of study drug. ^[3] Subject may be counted more than one row.

path\t program.sas date time

Programmer Note: Continue table for Eyelashes, Conjunctiva, Sclera, Cornea, Anterior Chamber Flare), Iris, Lens Status, Cataract Type, Grade.

Programmer Note: Continue table for Visits: Day1, Day2, Day3, Day7, Day14, Day 21, Day 28, Month 2, Month 3, Month 4, Month 5, Month 6, Month 9, Month 12/Early Term.

Programmer Note: Table 14.3.4.6.2 will contain the same information for the Non-Study Eye. Programmer Note: Denominators used for percentage calculation to be based on number of results reported for that perticular time point. Programmer Note: Table can be modified to align with information collected on the CRF.

Table 14.3.4.7 Fundus Photography by Eye Vitreous Examination **Safety Population**

	Cohort 1		Cohort	Cohort 2	
	0.5 x 10 ⁶ hRPC		0.5 x 10 ⁶ hRPC		Total ^[1]
	(N=)		(N=)		(N=)
Study Eye					
Baseline ^[2]	(n=)	(n=)	(n=)	(n=)	(n=)
Normal	n (%)	n (%)	n (%)	n (%)	n (%)
Abnormal, Not Clinically Significant	n (%)	n (%)	n (%)	n (%)	n (%)
Abnormal, Clinically Significant	n (%)	n (%)	n (%)	n (%)	n (%)
Non-Study Eye					
Baseline ^[2]	(n=)	(n=)	(n=)	(n=)	(n=)
Normal	n (%)	n (%)	n (%)	n (%)	n (%)
Abnormal, Not Clinically Significant	n (%)	n (%)	n (%)	n (%)	n (%)
Abnormal, Clinically Significant	n (%)	n (%)	n (%)	n (%)	n (%)

 [1] Total includes both Cohorts 1 and 2.
 [2] Baseline is defined as the value obtained at the baseline visit. If the baseline value is missing, the baseline value will be the last non-missing value recorded prior to the first dose of study drug. path\t program.sas date time

Programmer Note: Denominators used for percentage calculation to be based on number of results reported for that perticular time point.

	Cohc	Cohort 1		Cohort 2		
	0.5 x 10 ⁶ hRPC (N=)		0.5 x 10 ⁶ hRPC (N=)		Total ^[1] (N=)	
Baseline ^[2]						
n	n	n	n	n	n	

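### Acute cataract development or progression in phakic patients is a named safety criterion, but no SAP summary table estimates it

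*SAP*

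**What the plan says.** Protocol 3.2.2 lists the criteria used to establish safety. The slit-lamp item includes "acute cataract development or progression in phakic patients, vitreous haze". Protocol 8.1.5 repeats this as a purpose of the examination: "This assessment will include detection of anterior chamber cell or flare; acute cataract development or progression in phakic patients, or vitreous haze".

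SAP 10.7.1 summarises the lens in three separate pieces:

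- **Lens status:** "For lens status, subjects will be tabulated as aphakic, pseudophakic, and phakic".
- **Cataract type and grade:** "For cataract type, subjects will be tabulated as nuclear, cortical, posterior sub capsular, and not applicable. Subjects will also be tabulated by grades" of 1+ to 4+.
- **Eyes and timing:** "Results will be presented for each of subjects' eyes (study eye and non-study eye) at all time points".

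In SAP Appendix C, Table 14.3.4.6.1 covers the study eye and Table 14.3.4.6.2 repeats it for the non-study eye. The type rows include a *Not Applicable* row and carry the footnote "Subject may be counted more than one row". The grade rows run from +1 to +4, with no zero row and no *Not Applicable* row. The programmer note sets the percentage base: "Denominators used for percentage calculation to be based on number of results reported for that perticular time point". This fits the general rule in SAP section 5: "Percentages are routinely based on the total category count excluding the missing category if not otherwise mentioned".

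**The concern.** The protocol criterion has two parts: a change within an eye, and restriction to phakic patients. The planned tables supply neither. Separate counts at each visit do not show which eyes moved, and the grade rows are not crossed with lens status or with baseline grade.

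This matters because safety is the primary objective and cataract is a plausible event here. Protocol 1.1.1 says early cataract is common in RP. Exclusion criterion 11 in Protocol 4.2 rules out only recent or anticipated cataract surgery, so eyes operated on earlier can be enrolled and the sample may mix phakic and pseudophakic eyes. Change from baseline is planned for IOP (SAP 10.7.2), BCVA (9.1) and laboratory values (10.3). SAP 10.3 expects no laboratory concern because the product should stay in the eye. Cataract, which is an ocular risk, gets no change summary.

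**Working it through.** The plan states no cataract rate, power or target for this criterion, so there is no figure to reproduce. The planned size agrees with itself: 2 × (4 + 4 + 3 + 3) = 28 subjects, in cohort-by-dose cells of 3 or 4.

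**Step 1. Criterion against tables**

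| Needed by Protocol 3.2.2 | Planned in SAP 10.7.1 and Appendix C |
|---|---|
| Change within an eye | Counts at each visit, no change or shift |
| Phakic patients only | Results reported at the visit, any lens status |
| New cataract told apart from worsening | Type and grade counted separately, not linked to baseline |
| A meaning for *acute* | None in either document |

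No other section fills the gap. SAP 8.5 plans no subgroup analyses.

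**Step 2. Can the criterion be recovered from the planned rows?** Take an invented cohort of 14 study eyes, 9 phakic and 5 pseudophakic at baseline. Six phakic eyes have grades 1, 1, 2, 2, 2, 3, and three have none. Assume every cataract is nuclear, and that eyes without cataract or without a natural lens are ungraded and typed *Not Applicable*.

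- **History A.** One grade 1 eye rises to 2 and one grade 2 eye rises to 3. One grade 2 eye and the grade 3 eye have lens surgery. One ungraded eye develops grade 1. The rest are unchanged. Affected: 2 + 2 + 1 = 5, and 5/9 = 55.6%.
- **History B.** One grade 1 eye and one grade 2 eye have lens surgery. One ungraded eye develops grade 1. The rest are unchanged. Affected: 2 + 1 = 3, and 3/9 = 33.3%.

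| Rows at follow-up | Baseline | History A | History B |
|---|---|---|---|
| Phakic / pseudophakic | 9 / 5 | 7 / 7 | 7 / 7 |
| Nuclear / *Not Applicable* | 6 / 8 | 5 / 9 | 5 / 9 |
| Grade +1 / +2 / +3 | 2 / 3 / 1 | 2 / 2 / 1 | 2 / 2 / 1 |
| Eyes with a grade increase | – | 2 | 0 |

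Every planned row is the same in A and B, although two eyes worsened in A and none did in B. The type and grade rows barely move from baseline in either history.

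**Step 3. Surgery and the grade rows.** Take a cell of four phakic eyes graded 1, 2, 2, 3. The grade 3 eye has lens surgery and is no longer graded.

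- Grade 3 or worse: 1/4 = 25% before, 0/3 = 0% after.
- Mean grade (not a planned statistic, shown only for direction): (1 + 2 + 2 + 3)/4 = 2.00 before, (1 + 2 + 2)/3 = 1.67 after.
- Lens status: 4 phakic before, 3 phakic and 1 pseudophakic after.

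The grade rows improve because the worst eye has left them. The lens-status rows of the same table record the move.

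**The case against.** The strongest reply is that little is hidden. With at most 28 subjects, a reader can follow each eye through Listings 16.2.8.14.1 and 16.2.8.14.2, which give lens status, type and grade at every visit. Lens status is tabulated next to grade. Eyes expected to need cataract surgery within a year of treatment are excluded, so surgery during the 12-month follow-up should be uncommon. A cataract reported as an adverse event reaches the TEAE tables, and under Protocol 9.1 the condition that leads to a procedure is itself an adverse event. The study promises only descriptive summaries.

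Most of this stands and limits the point. It does not remove it. A listing is not a summary of a named criterion. Protocol 8.1.5 says the ophthalmic procedures are there to find eye events that ordinary reporting may miss, so adverse event tables cannot replace the slit-lamp summary. Those tables are not split by eye, the adverse event listing has no eye column, and they use no phakic denominator.

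Four stronger readings are tempting and not supported:

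- **Progression is diluted by non-phakic eyes.** No planned table reports a progression rate on any denominator, so there is no diluted figure. Ungraded eyes may simply fall out of the grade percentages. Only the type rows, with their *Not Applicable* row, could be affected, and not if all eyes are phakic. The phakic share is not given.
- **Surgery will be reported as improvement.** This holds only for the grade rows read in isolation.
- **The fellow eye is ignored.** Table 14.3.4.6.2 gives the same counts for it. What is missing is progression in fellow eyes set beside that in study eyes.
- **Cataract is the safety endpoint.** It is one item in a list of several, and it is qualified as acute.

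**Conclusion.** The point holds as a gap in the summaries: acute cataract development or progression among phakic eyes is a protocol safety criterion, and no SAP table estimates it. The conclusion follows from the text and table layouts and needs no numerical assumption. Its practical size is unknown, because the documents give neither the phakic share nor a cataract rate. The 3/9 against 5/9 contrast and the 1/4 to 0/3 shift are constructed illustrations, and the second assumes that an operated eye is no longer graded, which the SAP does not state. Because the data are listed by eye and visit, this is a worthwhile correction to the planned output, not a threat to the study's safety conclusions.

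**What to change.** Add one table restricted to eyes phakic at baseline, with study and fellow eyes side by side and each denominator printed. By visit, and at any time after injection, give the number of eyes with:

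- new cataract, where none was recorded at baseline;
- an increase of 1 or more in the recorded cataract grade;
- a change from phakic to pseudophakic or aphakic, counted as an event and not as missing;
- any of these.

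Add a shift from baseline to worst grade. Show the early visits separately, with the cut-off fixed in advance, so that the word *acute* is addressed. State which eyes receive a grade, and whether *Not Applicable* means a clear natural lens, no natural lens, or both. The listings show one cataract grade per eye per visit, so define the increase on that grade unless the CRF records a grade for each type. The slit-lamp listing has no surgery field, so the change in lens status has to stand in for surgery.

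The cost is one more table from data already listed. It should be specified before database lock, since SAP section 5 requires later additions to be labelled post hoc.
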